1. INTRODUCTION

In case of scheduled cesarean section, intrathecal anaesthesia, in the absence of contraindications, is the choice of anesthetic technique (1). This procedure is simple to perform and involves the administration of local anaesthetic with or without adjuvant, into the subarachnoidal space surrounding the spinal nerves and the spinal cord. It leads to a rapid onset of surgical anesthesia with a good quality motor and sensory nerve block to let the surgeons do their surgery in good conditions as well for the patient (2). So, it allows the parent, the mother in particular, to have a better experience of the delivery during the c-section.

Nevertheless, there are secondary effects due to this procedure and the local anaesthetics. Principally, haemodynamics effects such as major low blood pressure can decrease the utero-placental perfusion and cause nausea and vomiting (3,4). The outcome of the newborn is essentially related to the duration of maternal hypotension (5,6). Some prophylactic measures or treatments are taken, such as preloading perfusions, mother's position (left tilt) and the use of vasopressors drugs (ephedrine, phenylephrine) (3,4,7), but their efficacy remains questionable (8). Today, the studies' authors agree on the fact that the haemodynamics effects of the intrathecal injection are directly linked to the dose of the local anaesthetic (9).

For over 30 years, hyperbaric bupivacaine 0,5%, an amide-type local anesthetic of long action time, is the most used drug for spinal injection in c-section, associated to opioids (sufentanil or fentanyl and morphine) (10,11). However, its use is frequently followed by haemodynamical instability and by a motor nerve block of long duration, two factors that lead to an increased foetal risk and maternal discomfort (12).

The arrival on the market of newer short and intermediate duration time local anaesthetics such as chloroprocaine and prilocaine, seems to offer a good alternative for hyperbaric bupivacaine (13). This coincides with practice trends in anaesthesia for more ambulatory perioperative pathways and to a fast track rehabilitation in every speciality, obstetrics included.

Prilocaine, in particular, since its recent marketing into its stable hyperbaric form, has already been used for spinal injection in many studies in orthopedic surgery, gynaecologic surgery, and urologic surgery where it permitted a good quality nerve blockade with less secondary effects (14, 15). Its use, indeed, has shown a rapid onset anaesthesia (from 8 to 18 minutes maximum), a shorter action during time compared to the bupivacaine and a faster motor block offset in postoperative time, determined at 118 minutes (16).

In obstetrics, the former prilocaine isobaric form has been used only for epidural analgesia for the labour and vaginal delivery. Nevertheless, newborn high methemoglobinemia has been observed, due to long time epidural perfusion, at elevated doses in a range of 5,4-6,7 mg/kg (higher doses than 600mg) (17). Recently, hyperbaric prilocaine, without opioids adjuvants, has been used for c-section surgery in intrathecal injection in a pilot study realised to determine the efficacy dose 95 (ED95) (18). The results seem to be promising.

Until now, no study has ever compared prilocaine versus bupivacaine in spinal injection for c-section.

Our primary goal is to analyse the place of hyperbaric prilocaine 2% in a context of scheduled cesarean section by a power comparison study versus hyperbaric bupivacaine 0,5%, to find the most efficient one with a shorter action time and less secondary effects between this two local anaesthetics.

2. MATERIAL AND METHOD

It is a prospective, randomised (double blinded), multicentric study, with parturients undergoing scheduled cesarean section performed with intrathecal anaesthesia.

2.1. Population

Patients will be included in the study, after reading, understanding and accepting the document explaining the goals and the procedure of the study protocol and signing their consent. The study will proceed in the department of Anesthesiology-Reanimation of the CHU Saint-Pierre and in the department of Anesthesiology of the Hospital Sainte-Anne Saint-Rémi in collaboration with their respective department of obstetrics. The number of patients to be included in this study has been determined by a power study based on previous results. The trial will be end when a sample of 100 parturients will undergo a scheduled cesarean section performed with intrathécal anaesthesia.

The primary goal is to compare prilocaine with bupivacaine usually used in spinal injection; parturients will be assigned after randomisation into 2 groups:

- G1 : Hyperbaric Bupivacaine 10 mg (Marcaine®)
- G2 : Hyperbaric Prilocaine 50 mg (Tachipri ®)

To each dose will be added 2.5 µg of sufentanyl and 100 µg of morphine and the total injected volume will be identical for every group.

Inclusion criteria

- ASA < III
- Age 18-40 year
- Weight <110 kg
- Height between 160 and 175 cm
- Gestational age>37 SA
- Scheduled cesarean section
- Single fetus
- Non complicated pregnancy

Exclusion criteria

- Twin pregnancy
- History of 2 cesarean section or more
- Diabetes and gestational diabetes
- Placenta praevia

- Congenital foetale abnormality
- Patient in labour
- Membrane rupture
- Allergy to local anaesthetics
- Disagreement of the patient
- Gestational low blood pressure
- Pre eclampsia and eclampsia

2.2. Anaesthesia plan

Preoperative :

Patients will undergo a combined spinal and epidural anaesthesia, to allow for supplementation of the anesthesia in case incomplete or insufficient blockade.

2.2.1. Preoperative

- Premedication : PO ranitidine 300mg the day before, in the morning PO ranitidine 150mg and PO metoclopramide 10mg 30 minutes before the combined anaesthesia, PO citrate of sodium 30ml before the operating room.
- Coagulation test, full blood count, blood group, cross match and irregular antibodies check, and renal tests
- Miction before the operating room, evaluation of the bladder volume (Bladderscan) before the intrathecal anaesthesia in the operating room.

2.2.2. Peroperative

- Monitoring :

ECG, NIBP, pulse oximetry (SpO2), peripheral venous access 18G or 16G, urinary catheter, Bair hugger.

- Realisation of the combined anaesthesia :

Vascular co-loading with 1000ml of Hartmann solution.

The patient is in a sitting position, L3-L4 level is localised. With a Vygon combined anaesthesia set, the epidural space is reached with a Tuohy 8 cm needle, 17G with a low resistance syringe filled with saline. Then, a 29G needle is used through the Tuohy needle to access to the spinal space ; once the cephalo-spinal liquid reflux is positive, the test solution with 100 µg of morphine is injected into the spinal space in approximatively 20 seconds. Then an epidural multiperforated catheter is introduced until 3-4 cm in the epidural space, an aspiration test is done but no test dose is injected. The patient is placed, after 5 minutes minimum of the intrathecal injection, in supine position with a left tilt and 3l/min of nasal O2.

Every patient receive, after randomisation, a predetermined local anaesthetic dose (bupivacaine or prilocaine).

- Nerve blockade evaluation :

The evaluation of the sensitive level will be realised by a *pressure test*, a *cold test* and a *pin-prick test*.

The block will be considered as a :

- **SUCCESS** : bilateral T4 level reached in 15 minutes after intrathecal injection without additional epidural injection needed within 45 minutes peroperative ; no pain at the skin incision, no pain during 45 minutes after the skin incision.
- **FAILURE** : level < T4 at 15 minutes after the intrathecal injection or the additional epidural injection needed during the cesarean section (*lidocaine 2% with epinephrine*) by 5ml/5minutes for a VAS< 3.

- Low blood pressure evaluation :

As low blood pressure, we define a blood pressure lower than 20% or more than the basal blood pressure (Systolic BP before spinal anaesthesia).

Treatment : *Ephedrine 5mg/ml, phenylephrine 100 µg/ml* by titration (ml by ml); blood pressure goal : Systolic BP before spinal injection -10%.

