2.4.2. Central block (spinal injection)

- Sensitive block: level (pressure test, cold and pin-prick) every 2 minutes after spinal injection for 15 minutes, then every 5 minutes until the end of the surgery, then every 30 minutes until the complete release of the sensitive block (T12-S1) ;
- Time between spinal injection and reached of T4 level ;
- Obtained level 5 minutes after spinal injection ;
- Maximum sensitive level ;
- Complete lifetime of the sensitive block (as the period between maximun level and the regression to the level T12-S2) ;
- Lifetime of an adequate anesthesia for surgery (as the period between spinal injection and a VAS \geq 3 or a sensitive level superior regressed below T4 ;
- Lifetime of the complete anesthesia (as the period between spinal injection and a VAS \geq 0.
- Motor block: Modified Bromage score (from 1 to 6), before spinal injection, 10, 15, 20 minutes after injection, then every 15 minutes until the end of the surgery, then every 30 minutes until the complete released of the motor block (Bromage 6) ;
- Time of installation of the motor block (time between spinal injection and maximum motor block or Modified Bromage score of 1) ;
- Total lifetime of the motor block (time between maximal blockade/ Modified Bromage score 1 and a Modified Bromage score 6).

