2.4.3. Surgical variables

- Time between spinal injection and skin incision ;
- Time between spinal injection and placental delivery ;
- Time between skin incision and placental delivery ;
- Time between uterine incision and placental delivery ;
- Lifetime of the surgery.

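### Block SUCCESS and FAILURE are not complements: among women with bilateral T4 by 15 minutes, some can meet both definitions and some neither (minor)

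*Combined protocol and SAP*

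**What the plan says.** The nerve blockade evaluation in section 2.2.2 gives two labels.

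- SUCCESS has three parts. Level and supplement are covered by "bilateral T4 level reached in 15 minutes after intrathecal injection without additional epidural injection needed within 45 minutes peroperative", and pain by "no pain at the skin incision, no pain during 45 minutes after the skin incision".
- FAILURE is "level < T4 at 15 minutes after the intrathecal injection or the additional epidural injection needed during the cesarean section". The drug and its titration follow, ending "by 5ml/5minutes for a VAS< 3".

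Three other places bear on how these are read. Section 2.2 provides the epidural catheter "to allow for supplementation of the anesthesia in case incomplete or insufficient blockade". Section 2.4.2 collects the "Lifetime of an adequate anesthesia for surgery (as the period between spinal injection and a VAS" reaching 3 or more, or the level regressing below T4; that duration has no 45-minute limit. Section 2.4.3 collects "Time between spinal injection and skin incision" and "Lifetime of the surgery", but gives no expected value for either.

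No section ranks the two labels, adds a third category, or says that FAILURE means not SUCCESS.

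**The concern.** A two-way classification should give each woman exactly one label. Here the supplement clause is limited to 45 minutes in SUCCESS but covers the whole caesarean in FAILURE, and pain counts in SUCCESS only. Followed exactly, the rule can give a woman two labels or none. The success and failure rates then need not add to 100%, and someone would have to decide after the event which rate to report or how to place the ambiguous women.

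The overlap concerns late supplementation, which is relevant when one of the two drugs is described in the introduction as shorter-acting. It is better to settle the rule while the data are still blinded.

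**Working it through.** **Inputs.** The two definitions come from section 2.2.2. The total of 100 women in two groups comes from section 2.1, which gives no allocation ratio, so 50 per arm is an assumption.

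**Step 1: apply both definitions as written.** Take only women with bilateral T4 reached by, and present at, 15 minutes. This sets aside small wording differences between the two level clauses. Without T4 at 15 minutes a woman is a FAILURE whatever her pain.

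| Pain in the window | Supplement first needed | SUCCESS | FAILURE |
|---|---|---|---|
| No | Never | Yes | No |
| No | Within 45 min | No | Yes |
| No | After 45 min, still in surgery | **Yes** | **Yes** |
| Yes | Never | **No** | **No** |
| Yes | Within 45 min | No | Yes |
| Yes | After 45 min, still in surgery | No | Yes |

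Four of the six patterns get one label, one gets both and one gets neither. The third row can occur only if surgery outlasts the window. A pain-free woman first supplemented at 50 minutes of a 70-minute operation falls there, but no woman can if the operation lasts 40 minutes. The fourth row does not depend on duration.

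**Step 2: how wide is the fourth row?** It depends on when a supplement counts as needed and on what no pain means.

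- Needed at VAS 3 or more (the cut in section 2.4.2), no pain meaning VAS 0: only VAS 1-2 is unclassified.
- Needed at VAS 3 or more, no pain meaning VAS below 3: the row is empty.
- No link between VAS and need: any pain without a supplement is unclassified.

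VAS is recorded every 5 minutes during the operation (section 2.4.6), so mild pain would appear in the data.

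**Step 3: effect on the rates.** For an arm of n women,

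SUCCESS rate + FAILURE rate = 100% + (number meeting both - number meeting neither)/n.

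At n = 50, one woman is 1/50 = 2.0 points. If the split were 60:40, she would be 1/60 = 1.7 or 1/40 = 2.5 points. Two invented arms of 50 show the mechanics; they are not forecasts.

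- 46 SUCCESS only, 3 FAILURE only, 1 both: 47/50 = 94% and 4/50 = 8%, total 102%. Success taken as 100% minus failure would be 92%.
- 46 SUCCESS only, 3 FAILURE only, 1 neither: 46/50 = 92% and 3/50 = 6%, total 98%. Success taken as 100% minus failure would be 94%.

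**Step 4: start of the supplement window.** The 45-minute supplement limit has no stated start, while the pain window starts at incision. Let t be the time from injection to incision. If the supplement window runs from injection, it ends at minute 45 and the pain window at minute t + 45, a gap of t. With t assumed to be 10 to 20 minutes, the gap is 10 to 20 minutes. It matters only for a supplement needed without pain in that gap, since pain there already rules out SUCCESS.

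**The case against.** The strongest reply is that no planned result depends on this. The definitions sit in the anaesthesia plan, block success is not listed in section 2.4, and section 2.3 specifies no analysis of it. The primary outcome is how long the motor block takes to resolve. That stands, and it keeps the point minor. The stated aim of finding the more efficient drug makes a success rate a plausible report, not a planned one. Freedom to choose a version after the event is also not special to this variable, because the plan specifies no analysis for any secondary one.

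A second reply is that any reader will take a woman who misses SUCCESS as a FAILURE. This is a reasonable inference for the fourth row of the table, although the text does not state it. It does not settle the third row, where the same woman satisfies every clause of SUCCESS and one of FAILURE.

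A third reply is that the neither group is narrow, and may be empty, once need and freedom from pain are read at VAS 3. That also stands as a possible reading. Section 2.4.2 separately defines complete anaesthesia, however, so the strict reading of no pain remains open.

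The unstated window start adds little. The neighbouring pain clause suggests incision as the origin.

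A reader might also take "by 5ml/5minutes for a VAS< 3" as a supplement trigger that contradicts section 2.4.2. The documents do not require this: it can be read as the target of the titration, and then the two sections agree.

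**Conclusion.** The two definitions contradict each other as a classification, and no other section repairs this. The logic rests on the text alone. The overlap also needs surgery to outlast the window, and the gap needs a strict reading of no pain or a supplement threshold above the pain recorded. The size is 2 points on an arm's rate per ambiguous woman at an assumed 50 per arm.

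A reader might infer that the rule biases the comparison because prilocaine is described as shorter-acting. The documents do not support that. They give no surgery duration and no expected frequency of late supplements or mild pain, so neither the number of women nor a direction can be derived. Wear-off is in any case captured by the duration of adequate anaesthesia in section 2.4.2, although that does not decide the binary label. Nor does the defect touch the primary outcome. Minor.

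**What to change.** Before unblinding, and for classification only:

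1. Define FAILURE as not SUCCESS.
2. Use the same supplement window in both. One workable choice counts any supplement needed during the caesarean, as FAILURE already does, and keeps the existing pain window from skin incision. Report the 45-minute version as a sensitivity analysis, with its start stated.
3. State whether no pain means VAS 0 or a VAS below the cut of 3 in section 2.4.2.
4. Record whether a supplement was needed and when. Section 2.4 does not name it.

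The cost is a short wording change and one added data item. Sensory level and VAS are already collected every 5 minutes during surgery, as are the injection-to-incision time and the length of surgery, so either time origin can be derived.

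There are two downsides, both at an assumed 50 per arm. Compared with the 45-minute version, an arm's success rate falls by 2 points for each woman first supplemented late. If no pain stays strict, its failure rate rises by 2 points for each woman with pain only, including those at VAS 1-2. Keeping the present pain window means that late pain without a supplement changes no label.

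No change to when any woman is supplemented is proposed.

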2.2.3. Postoperative

- Postoperative analgesia : Paracetamol + NSAID at the end of the surgery.
- Removal of the urinary catheter : after complete offset of the motor block and a stand up trial (after a forced extention of the legs against resistance, about 3 hours after the intrathecal injection) ; and/or S2 level restored.
- Monitoring of the bladder volume 1x/hour, by Bladderscan examination until first miction.

In case of bladder retention, defined such as a bladder volume higher than 600ml, associated at a spontaneous miction, a bladder catheterisation will be realised.

- Walking : it will be asked to the patient to do a walking test (6 minutes walking test) with a minimum of 25 m to walk, 1h, 2h, 3h and 4h after a complete released of the motor block and a sensitive block lower than L5-S1.

2.3. Statistical analysis method

The primary outcome that will be analysed in this study is the time to motor block resolution after intrathecal injection of the two local anaesthetics.

Every patient will receive, after randomisation, a dose of local anaesthetic (bupivacaine or prilocaine); the study will be powered to highlight a difference of 20% for the principal variable between the groups.

2.4. Collect of the data

2.4.1. Patients

- Name, number of file, age, weight, height, BMI, parity/gestity, ethnicity, number of previous c-section, term.
- Blood pressure, cardiac frequency, pre operatory SpO2 and before anaesthesia.
- Bladder volume before Spinal injection.

2.4.2. Central block (spinal injection)

- Sensitive block: level (pressure test, cold and pin-prick) every 2 minutes after spinal injection for 15 minutes, then every 5 minutes until the end of the surgery, then every 30 minutes until the complete release of the sensitive block (T12-S1) ;
- Time between spinal injection and reached of T4 level ;
- Obtained level 5 minutes after spinal injection ;
- Maximum sensitive level ;
- Complete lifetime of the sensitive block (as the period between maximun level and the regression to the level T12-S2) ;
- Lifetime of an adequate anesthesia for surgery (as the period between spinal injection and a VAS \geq 3 or a sensitive level superior regressed below T4 ;
- Lifetime of the complete anesthesia (as the period between spinal injection and a VAS \geq 0.
- Motor block: Modified Bromage score (from 1 to 6), before spinal injection, 10, 15, 20 minutes after injection, then every 15 minutes until the end of the surgery, then every 30 minutes until the complete released of the motor block (Bromage 6) ;
- Time of installation of the motor block (time between spinal injection and maximum motor block or Modified Bromage score of 1) ;
- Total lifetime of the motor block (time between maximal blockade/ Modified Bromage score 1 and a Modified Bromage score 6).

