2.4.6. Secondary effects

- Pain: VAS at incision time, placental delivery time, peritoneal closing time, skin closing time and every 5' during the c-section, then every 4 hours for 24h ;
- Nausea/ Vomiting, Headache, Prurit from 15 minutes after spinal injection, then every 4 hours for 24h ; marked as : 0= no symptoms ; 1= symptoms with no treatment necessary ; 2= Symptoms present and treated ;
- Total blood loss (ml) ;
- Transient neurologic symptoms at D0, D1, D3 and D15, Defined as pain or dysesthesia or both, showed after complete released of the block in the lower limbs (19).

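### The sensory and VAS reading intervals widen sharply at the end of surgery, so the secondary anaesthesia durations carry interval-censoring error, of no fixed direction, that section 2.3 does not address

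*Combined protocol and SAP*

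**What the plan says.** Section 2.4.2 sets the sensory readings at every 2 minutes for the first 15 minutes, "then every 5 minutes until the end of the surgery, then every 30 minutes until the complete release of the sensitive block". Section 2.4.6 sets VAS at named surgical moments, including "skin closing time and every 5' during the c-section, then every 4 hours for 24h".

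Three durations in section 2.4.2 depend on these readings:

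- Adequate anaesthesia: "Lifetime of an adequate anesthesia for surgery (as the period between spinal injection and a VAS" of 3 or more, or "a sensitive level superior regressed below T4". It uses both schedules.
- Complete anaesthesia: "Lifetime of the complete anesthesia (as the period between spinal injection and a VAS" of 0 or more, as printed. It uses the VAS schedule alone.
- Sensory block: "Complete lifetime of the sensitive block (as the period between maximun level and the regression to the level T12-S2". It uses the level schedule alone.

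Section 2.3 names time to motor block resolution as the primary outcome and a 20% difference as the target. It gives no rule for dating an event that occurs between two readings and no method for interval-censored times. The Introduction expects prilocaine to have "a shorter action during time compared to the bupivacaine".

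**The concern.** An event is only known to lie between the last reading without it and the first reading with it. If the time of the first positive reading is taken as the event time, every duration is recorded late by an amount set by the reading interval. At the end of surgery that interval grows 6-fold for level (30/5) and 48-fold for VAS (240/5).

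If one drug wears off sooner, the two arms can have different shares of events on the fine and coarse schedules, or fall in different places within one 4-hour gap. The recording delay then differs by arm. Randomisation and blinding do not remove this, because the difference arises from the event times themselves. At stake is whether the reported difference in duration of anaesthesia measures the drugs or partly the timetable. Readings not taken cannot be recovered at analysis.

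**Working it through.** The plan gives no figure for these durations to reproduce; its sample of 100 relates to the motor-block outcome.

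**Inputs from the documents.** Level interval 5 then 30 minutes (2.4.2). VAS interval 5 then 240 minutes (2.4.6).

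**Assumptions, since the documents are silent.** Surgery ends 65 minutes after injection (SD 10). Event times are normal with SD 10, 20 or 30 minutes. Each event is recorded at the next reading. The 4-hourly series runs from the end of surgery.

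**Level schedule, by hand.** If events are spread evenly within an interval, the mean delay is half of it: 5/2 = 2.5 minutes in surgery and 30/2 = 15 after. With shares pP (prilocaine) and pB (bupivacaine) of events falling in surgery:

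inflation = (15 − 2.5) × (pP − pB) = 12.5 × (pP − pB)

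The ceiling is 12.5 minutes, when all prilocaine events fall in surgery and all bupivacaine events after it. With assumed shares of 75% and 25%, the mean delays are 0.75 × 2.5 + 0.25 × 15 = 5.6 and 0.25 × 2.5 + 0.75 × 15 = 11.9, an inflation of about 6.3. With both shares at 0, it is 0.

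**VAS schedule, by hand.** Half of 240 is not a usable mean delay, because events need not be spread evenly over so long a gap. With surgery ending at 65 minutes, the postoperative readings fall at 65 + 240 = 305, then 545.

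- True times 200 and 240: both recorded at 305. Delays are 105 and 65, and a true 40 becomes 0.
- True times 280 and 340: recorded at 305 and 545. A true 60 becomes 240.
- True times 50 and 90: the first is caught within 5 minutes, the second is recorded at 305, a delay of 215.

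**Simulation** (400,000 draws per arm). The table shows bias in the bupivacaine-minus-prilocaine difference, recorded minus true, in minutes, over SD 10 to 30:

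| Assumed means, prilocaine v bupivacaine | Level schedule | VAS schedule alone |
|---|---|---|
| 50 v 90 | +5.5 to +9.4 | +89 to +170 |
| 60 v 75 | +2.2 to +4.7 | +36 to +86 |
| 100 v 120 | −0.2 to +0.9 | −18 to +4 |
| 120 v 150 | 0 to +0.3 | −30 to −21 |
| 200 v 240 | about 0 | −40 to −35 |
| 280 v 340 | about 0 | +96 to +169 |

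The formula agrees with the level column. For 50 v 90 at SD 10 the simulated shares in surgery were 0.86 and 0.04, so 12.5 × 0.82 = 10.3, against 9.4 simulated. At 200 v 240 on the VAS schedule, the recorded difference was 0 to 5 against a true 40.

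**Composite.** Adequate anaesthesia ends at pain or at loss of T4, whichever is found first. Level is still read every 30 minutes until the sensory block has gone, so loss of T4 is normally found within 30 minutes even when no VAS is due. The large VAS figures therefore apply to complete anaesthesia, not to this outcome.

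**The case against.** A reader might infer that the schedule always enlarges the drug difference, because prilocaine is expected to wear off first and so be read on the fine schedule. The documents do not support that. They state no surgery length, no time to loss of T4 and no time to first pain. The 118-minute figure in the Introduction is a motor offset, and the 45-minute window in section 2.2.2 defines block success, not length of surgery. When both arms' events fall after surgery the level bias is about 0, and the VAS schedule can hide a real difference. A fixed ceiling of 120 − 2.5 = 117.5 minutes for VAS is also unsupported, since it needs events spread evenly over the gap.

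Three further points count against giving this much weight. The outcomes are secondary. The primary outcome has its own schedule of every 15 minutes later in surgery and every 30 minutes afterwards. With identical event-time distributions in the two arms, the expected delays are equal, so the schedules do not create an effect from nothing.

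All of this stands, and it limits the point to one about the size of secondary estimates. It does not remove it: the plan still has no rule for timing these events, and an estimate that can lose 40 minutes or gain more than an hour, depending on where a reading falls, cannot support a statement about duration.

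**Conclusion.** The point holds as a worthwhile, inexpensive improvement to secondary outcomes. The durations resting on sensory level and VAS have interval-censoring error that changes abruptly at the end of surgery and is left unhandled.

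- **Level-based durations:** inflation of up to about 12.5 minutes on average if the arms straddle the end of surgery (about 2 to 9 simulated), and about 0 otherwise. Loss of T4 near the end of surgery is plausible. Regression to the lowest levels would show little bias if it falls after surgery in both arms.
- **Complete anaesthesia:** error of either sign that can exceed an hour.
- **Adequate anaesthesia:** the delay is normally limited by the 30-minute level readings.

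The documents supply only the intervals. The event times, their spread, the surgery length and the start of the 4-hourly series are assumptions, so the figures show what can happen and do not forecast this trial. It would be wrong to conclude that the primary comparison is compromised by these schedules.

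Separately, the printed VAS threshold for complete anaesthesia, 0 or more, is met by every reading. That duration is undefined until the threshold is corrected.

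**What to change.** 1. In 2.4.6, add a VAS at each 30-minute postoperative sensory check until pain meeting the VAS endpoints has been read or those checks end.
2. In 2.4.2, record two times for each duration: the last reading without the event and the first reading with it.
3. In 2.3, state that these durations are analysed as interval-censored, name the model and effect measure, and treat patients without the event at their last reading as right-censored.
4. In 2.4.2, correct the VAS threshold for complete anaesthesia, and reconcile the end level of the sensory block, given as T12-S1 in one line and T12-S2 in another.

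The cost is one extra bedside question at visits already planned, a few sentences and slightly more analysis work with standard software.

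One limit remains. All patients receive intrathecal morphine, and analgesics at the end of surgery, so pain may first appear after the sensory checks stop. It would then still be timed only to within 4 hours. The interval-censored analysis should carry that width openly.

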2.4.7. Post-operative analgesia

- Lifetime between the first administration of analgesic drugs after the spinal injection, doses of the administrated drugs by day et total of injections for 72h.

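### Two collected duration items need repaired end points: complete anaesthesia ends at a VAS that every score meets, and the first-analgesic interval is unfinished and silent on the scheduled dose

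*Combined protocol and SAP*

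**What the plan says.** Section 2.4.2 lists several durations to be recorded. One is "Lifetime of an adequate anesthesia for surgery (as the period between spinal injection and a VAS \geq 3", or until the sensory level falls below T4. The next is "Lifetime of the complete anesthesia (as the period between spinal injection and a VAS \geq 0".

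VAS is scheduled in section 2.4.6: "Pain: VAS at incision time, placental delivery time", at peritoneal and skin closing, and "every 5' during the c-section, then every 4 hours for 24h". Section 2.2.2 makes it part of a successful block that there is "no pain at the skin incision, no pain during 45 minutes after the skin incision".

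Section 2.4.7 records "Lifetime between the first administration of analgesic drugs after the spinal injection", followed by daily doses and the total number of injections over 72 hours. Section 2.2.3 gives "Postoperative analgesia : Paracetamol + NSAID at the end of the surgery". For insufficient anaesthesia in theatre, section 2.2.2 provides epidural lidocaine and counts "the additional epidural injection needed during the cesarean section" as a failure.

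For the sensory block, section 2.4.2 continues the readings until release at T12-S1, but ends the block's lifetime at regression to T12-S2.

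The only outcome given a rank is the primary one, resolution of the motor block (section 2.3). The items above are listed as data to collect. The plan does not call them secondary and specifies no analysis for them.

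**The concern.** The Introduction says that the trial seeks, among other things, the agent with the shorter action. Items that time the end of anaesthesia or the first need for analgesia bear on that aim, so their end points should be events that depend on the block wearing off.

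As written, the end point of complete anaesthesia does not depend on the block at all. The first-analgesic interval may also not depend on it, according to how the unfinished sentence is completed. If so, a difference between arms in these items would say how soon or how long the women were operated on, not how long the drug acted. Some of the loss could be permanent: if scheduled and requested doses are not told apart when they are recorded, the distinction may not be recoverable later.

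**Working it through.** The plan gives no figure for these items, so there is nothing to reproduce. The check compares the definitions with the schedules.

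**(a) Complete anaesthesia**

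1. The lowest possible VAS score is 0, so VAS ≥ 0 is true of every reading.
2. The end event is therefore met at the first VAS taken. The first reading scheduled in section 2.4.6 is at skin incision.
3. The recorded value becomes spinal injection to skin incision, which section 2.4.3 already lists as a separate variable.
4. Section 2.2.2 requires a successful block to be pain-free at incision and for 45 minutes afterwards. With no pain taken as VAS 0, such a woman's first non-zero score comes more than 45 minutes after incision. Shortfall = (time of first VAS > 0) − (time of incision) ≥ 45 minutes.
5. At one reading every 5 minutes, 45 / 5 = 9 further zero readings would follow the recorded end of her complete anaesthesia, if surgery lasts that long.
6. With the end event changed to VAS > 0, the time is located to within about 5 minutes during surgery. After surgery, readings are 4 hours apart for 24 hours (24 / 4 = 6 readings). For a woman still at 0 at skin closing, the event is then known only to lie between two readings up to 4 hours apart. It also falls after the analgesia scheduled for the end of surgery.

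**(b) First analgesic**

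1. The sentence in section 2.4.7 opens an interval but gives only one event tied to a reference time. One completion is spinal injection to first analgesic.
2. On that completion, with no exclusion, the dose scheduled in section 2.2.3 counts.
3. For any woman given that dose as scheduled: interval ≤ (spinal injection to incision) + (duration of surgery), approximately. Both terms are listed in section 2.4.3. This assumes that duration of surgery runs from skin incision, which the plan does not say.
4. With no earlier analgesic, the interval is about equal to that sum. If epidural lidocaine counts and was given, the interval is shorter still. In neither case can it extend beyond about the end of surgery.
5. The proportion of women given the dose as scheduled cannot be computed from the documents.

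**(c) Sensory block**

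The two levels differ by one segment. If regression to S2 means that S1 has been released, stopping the readings at T12-S1 and ending the lifetime at T12-S2 can be the same event. If S2 itself must be released, readings may stop before the end point is seen. Section 2.2.3 uses S2 for catheter removal and section 2.4.9 uses L5-S1 for walking; neither settles which reading is meant.

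**The case against.** The best defence of (a) is that the intent is plain. The line follows adequate anaesthesia, which ends at VAS ≥ 3, so complete anaesthesia presumably ends at the first non-zero score. The sign may be a slip of one character, or a fault in converting the PDF. This stands in part: the source must be checked first, and the 45 minutes describe only what happens if the rule is followed literally. They are not an expected loss in the trial. Still, staff at two hospitals will collect the item, and its definition should not rely on a guess.

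It can also be said that changing the sign is not a full repair, because the postoperative readings are sparse and follow scheduled analgesia. That is correct and is dealt with in the fix.

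On (b), the sentence is broken, so no single reading can be called the intended one, and the doses collected over 72 hours describe analgesic use separately. Both points stand. What remains is that the interval is incomplete and does not say whether the scheduled dose counts.

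On (c), no loss is shown.

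A reader might go further and infer that the trial cannot compare duration of action. The documents do not support this: motor block, adequate anaesthesia and the walking tests also cover it. A reader might also infer that the scheduled dose ends the analgesic interval in most women, but the documents give no figure for how many receive it as scheduled or need something earlier.

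**Conclusion.** The concern holds for two collected items and is minor.

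- **Complete anaesthesia.** If the sign is as printed, the item ends at incision and conflicts with the pain-free success rule. The shortfall is at least 45 minutes for any woman meeting that rule. This rests on a literal reading and on taking no pain as VAS 0.
- **First analgesic.** The definition is unfinished. Read as spinal injection to first analgesic, it is capped at about the end of surgery for every woman given the scheduled dose. Their number is unknown.
- **Sensory block levels.** This is an editorial mismatch with no demonstrated loss.

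The primary outcome and the sample size are untouched. It would be wrong to present this as a flaw in the trial's secondary endpoints, since the plan ranks none of these items and specifies no analysis of them.

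**What to change.** 1. **Section 2.4.2, complete anaesthesia.** Check the sign in the source document. If it is ≥ 0, change it to the first VAS > 0. For women still pain-free at skin closing, report the time as interval-censored between the last zero and the first non-zero reading, and note that those readings follow scheduled analgesia. A woman with no non-zero score by the last reading is right-censored there.
2. **Section 2.4.7, first analgesic.** Complete the definition as spinal injection to the first analgesic given on request or for pain. Mark each dose as scheduled or on request, and state whether epidural lidocaine counts. Any report should note that both arms also receive intrathecal sufentanil and morphine (section 2.1), so this time reflects those drugs as well as the local anaesthetic.
3. **Section 2.4.2, sensory block.** Reconcile T12-S1 and T12-S2 so that readings stop at the same named level that ends block lifetime.

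The cost is a few words in two sections and one extra data field per analgesic dose. No additional assessments are needed, and the sample size and primary analysis do not change.
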